The primary objective of this application is to determine the efficacy of percutaneous intramuscular (IM) peripheral nerve stimulation (PNS) in reducing shoulder pain secondary to SIS refractory to conservative management. IM PNS involves the percutaneous placement of a single IM electrode to stimulate the axillary nerve motor points of the deltoid muscle. The PI and collaborators developed the technique and completed a case series to demonstrate its feasibility for the treatment of SIS. [18, 19] Unlike spinal cord stimulation [20, 21], peripheral nerve field stimulation [22, 23] and transcutaneous electrical nerve stimulation (TENS) [24], IM PNS can maintain pain reduction for up to 12-mo after cessation of stimulation. IM PNS is proposed as an alternative to surgical subacromial decompression, which may be less risky, less costly and more effective. We propose a multisite, double-blinded, placebo-controlled RCT of percutaneous IM PNS for the treatment of refractory SIS in those with SIS with outcomes focusing on pain reduction, shoulder impairment, activities of daily living (ADLs) and quality of life (QoL).

The secondary objective is to investigate the mechanism underlying IM PNS mediated pain reduction. First, the initiation of SIS is likely due to the repetitive trauma of the supraspinatus tendon and subacromial bursa by the undersurface of the acromion resulting in nociceptive pain [25]; however, as patients fail conservative management and pain becomes more chronic, central sensitization may have the more dominant role. [26-29] To evaluate the role of IM PNS in reducing central sensitization, an assessment of the sensory system is proposed using mechanical and thermal quantitative sensory testing. Second, this study will also determine the phenotype that differentiates responders from non-responders. It is known that pain perception is influenced by multiple factors and not reliant on structural pathology alone, thus psychological traits, mood, demographics, physical examination, structural anatomy, and sensory testing will be measured. Determining the phenotype of responder will provide insight into mechanism, as well as improve patient selection for treatment.

7.2 * What are the specific aims of this study i.e. what are the question(s) this research intends to answer? Provide at a maximum 3 primary and 3 secondary aims.

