AIM 1: Determine the Efficacy of IM PNS in Treating SIS Refractory to Conservative Management. The trial will enroll 116 participants who will be treated for 7-wks with IM PNS or placebo and followed for 6-mo.

Hypothesis 1: The IM PNS participants will experience greater pain reduction and shoulder impairment, and greater improvements in ADLS and QoL than controls.

This is your Hypothesis also known as your aims (NIH) or safety and efficacy aims (industry). Please list no more than 3 primary and 3 secondary clearly label these aims primary and secondary.

AIM 2: Quantify the Relationship between IM PNS Mediated Pain Reduction and Central Sensitization. As an initial step toward determining the role of IM PNS in modulating central sensitization, pain thresholds will be characterized using mechanical and thermal quantitative sensory testing.

Hypothesis 2: Pain thresholds will increase in the IM PNS group relative to controls at the affected shoulder (primary hyperalgesia) AND at the contralateral shoulder or tibialis anterior (secondary hyperalgesia).

AIM 3: Determine the specific phenotype characteristics will differentiate responders to IM PNS from non-responders. Baseline measurements of psychological traits, mood, demographics, physical examination, structural anatomy, and sensory testing will be utilized to determine the phenotype of those subjects who have successful pain relief from treatment with IM PNS.

Hypothesis 3: Specific phenotype characteristics can be identified to differentiate responders to IM PNS from non-responders.

7.3 Please provide a summary of the present knowledge relevant to the research and make citation to any applicable scientific literature:

See attached.

This is your literature search and bibliography. Also known as Background and significance (NIH) or Introductory Section from industry sponsored trial.

If it is easier to attach your response to question 7.3 please do so here. Please limit to three pages.

7.4 Option to Upload Documents related to question 7.3:

Name

[PNS for SIS 8 week/60 day tx justification](#) | [History](#)

[PNS for SIS Background and Prior Studies](#) | [History](#)

[PNS for SIS References](#) | [History](#)

Description

View: 08-00 Methods and Procedures I

8.0 Methods and Procedures I:

8.1 Will this research involve the following Social-Behavioral Procedures:

Name

Surveys/Questionnaires

Check all that apply.

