8.2 Will this research involved any of the following Medical Procedures/Considerations:

Check all that apply.

Name
Collection of Biohazardous Substances
Study of Human Biological Materials (i.e. Urine Collection)
Investigation/Approved Devices
Study of Existing Data
Medical Tests, Comparisons, Evaluations
Clinical Assessments (EEG, EKG, SCID, etc.)
Venipuncture (Blood Draw)
Magnetic resonance imaging (MRI) without contrast
Use of investigational devices

8.3 Identify Data Collection types for this study:

Name
Audio-Recording/Video-Recording/Photographs
Chart Review - Prospective
Existing/Retrospective Data/Specimens
Interviews, questionnaires or psychological tests

Check all that apply.

Note if you are doing, recordings, Video-Recording/Photographs then subjects will need to sign the MetroHealth Audio-Video Consent form. See the IRB Forms and Templates.

View: 08-01 Methods and Procedures II

8.1 Methods and Procedures II:

8.4 * Please specify in detail the methods and procedures that are involved in this research:

Study Summary: This is a multi-site, placebo controlled, double-blinded RCT that evaluates the efficacy of a new treatment for chronic shoulder pain to conservative management in otherwise healthy adults. One-hundred-sixteen participants are randomized to receive IM PNS or placebo treatment. All participants receive a single IM lead, and receive 6-hrs of daily PNS for 7-wks. The IM PNS group receives active stimulation while the control group receives placebo stimulation. All participants will also receive a course of PT during the treatment period to improve upper limb function and prevent re-injury by educating and training participants in the biomechanics and proper use of the shoulder and the upper limb. Measures of pain, shoulder impairment, pain interference with ADLs, ADLs, QoL and pain thresholds are assessed at baseline, time of implantation, at the start of treatment, at the EOT, 12, 24-wks treatment..

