Baseline Variables and Randomization: Baseline data are collected so that the balance of covariates across the two groups can be evaluated. Each participant is characterized with respect to pain-related psychological traits, mood, demographics, comorbidities, and medication use. All participants will undergo a MRI(unless they are available in the ipsilateral shoulder) to evaluate for rotator cuff tears, tendonopathy and subacromial bursa fluid. Study outcome measures (see Outcomes Assessment) are administered to establish baseline levels. Participants are assigned to treatment groups using a stratified, block randomization scheme to minimize group imbalances on key patient characteristics: site, baseline pain (> 6 or ≤ 6), duration of pain (≥ 18 months or < 18 months). The randomization sequence is contained within the RedCap database..

If this field is not completed your protocol will not be reviewed. Do not enter N/A. Please describe what methods and procedures will be involved in this research.

Percutaneous IM PNS System: The Sprint PNS System (SPR Therapeutics, Cleveland, OH) is used to deliver the IM PNS. The System consists of a small external stimulator, percutaneous IM lead, and pad. The external stimulator “snaps” on to the pad. The pad serves as the anode. The pad is replaced regularly based on treatment parameters, allowing the investigative team to prescribe the total dosage based upon the number of pads. The single-channel stimulator outputs a biphasic current waveform with current pulse parameter ranges that are suitable for IM PNS. The IM electrode, originally developed at the Cleveland FES Center, has a coiled helical configuration wound from a 7-strand type-316LVM stainless-steel wire insulated with a poly-fluorocarbon, similar to Teflon®. These electrodes have been used extensively to deliver percutaneous IM PNS to shoulder muscles. [19, 36, 37, 39-42, 62, 75]

Lead Placement Procedure:

IM PNS Group: The procedure is performed under a sterile condition. The location and depth of the electrode implant site are determined by monopolar needle stimulation with demonstration of strong contraction of both the middle and posterior deltoid muscles. [18, 19, 39, 42] The introducer loaded with the IM lead is inserted perpendicular to the skin surface and advanced to the depth (3-4 cm) defined by the monopolar test stimulation. The introducer is then withdrawn with the electrode retained in the muscle by a barb at its tip.

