Visit 13 – End of Treatment + 24 wks Outcomes Assessment: Skin checked. Study outcomes assessment measures administered. Subject queried for medication usage and adverse events. (~2 hrs)

Provision for lead replacement: If, in the judgement of the Investigator, the Sprint MicroLead becomes significantly displaced or fully dislodged, it is possible that the Investigator may elect to place another lead which would require an unscheduled visit. Other visits may be repeated as appropriate.

Unscheduled Visits are conducted if/as needed.

*some visits may be combined to accommodate subject or staff scheduling

*Visits may be completed via telephone, telehealth or email as determined by the principle investigator in case of immediate hazard to the subject

Check yes or no.

This is also known as NIH Experimental Procedure section or Clinical Trial Procedure/Experimental Flow section. Do not just attach documents in response to this question you must do a study design summary for IRB Review.

*Visits 12 and 13 : These visits include questionnaires and can be completed via telehealth, telephone or email at the discretion of the PI

Email will only be used with subject who sign the Alternative Means HIPAA

8.7 Please attach study design/subject visit schedule here:

Name

[PNS for SIS Visit Schedule Table](#) | [History](#)

Description

If you have an electronic schedule of study visits and/or procedures please attach here.

View: 09-00 Inclusion/Exclusion Criteria

9.0 Inclusion/Exclusion Criteria:

9.1 What are the inclusion criteria? Put this information in bullet form:

- Shoulder pain of >3 months
- Age>=21-90
- Worst pain in the last week>=4 (0-10 scale)
- Ability to check skin and perform dressing changes, independently or with assistance
- Stable dose of pain medication (Not taking more than 1 opioid or 1 non-opioid analgesic)

Please list inclusion criteria.

9.2 What are exclusion criteria? Put this information in bullet form:

- Current shoulder joint or overlying skin infection, or current bacterial infection requiring antibiotics
- Other chronic pain syndrome (Pain in another area of the body 15 or more days in the last 30 (more than half of the time) or taking daily analgesics for another pain syndrome)
- Prior shoulder surgery to ipsilateral shoulder joint (glenohumeral, rotator cuff, AC joint, etc.)
- Corticosteroid injection in the ipsilateral shoulder or any pain relieving procedure at the shoulder in the last 12 weeks

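### Aim 3 and Hypothesis 3 name no placebo comparison, so a responder contrast read as worded cannot attribute differences between patients to stimulation

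*Combined protocol and SAP*

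**What the plan says.** Section 7.2 sets out three aims. Hypothesis 1 compares IM PNS participants with controls. Hypothesis 2 also names the comparator: "Pain thresholds will increase in the IM PNS group relative to controls at the affected shoulder". Aim 3 does not. It says that baseline measurements "will be utilized to determine the phenotype of those subjects who have successful pain relief from treatment with IM PNS", and Hypothesis 3 reads "Specific phenotype characteristics can be identified to differentiate responders to IM PNS from non-responders".

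The statement of the secondary objective, just before section 7.2, gives the use to be made of the result: "Determining the phenotype of responder will provide insight into mechanism, as well as improve patient selection for treatment".

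Section 8.4 (Study Summary) gives both arms an active co-intervention: "All participants will also receive a course of PT during the treatment period". Section 8.4 (Baseline Variables and Randomization) records most of the candidate traits in both arms: "Each participant is characterized with respect to pain-related psychological traits, mood, demographics, comorbidities, and medication use".

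Section 10.3, on outcomes, methods and power, refers to attachments. The outcomes and data analysis attachment listed in section 10.4 is not in the text available for this review.

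**The concern.** Selecting patients for stimulation, or learning how it works, requires knowing whose outcome is better with stimulation than it would have been without it. Improvement in the IM PNS arm mixes three things: the effect of stimulation, the effect of the physical therapy given to everyone, and the placebo response to an implanted lead and a worn device. A trait that predicts either of the last two will separate responders from non-responders in that arm just as well as a trait that modifies the effect of stimulation.

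Hypothesis 3 could therefore be confirmed truthfully and still mislead. A clinic might choose patients for a percutaneous lead using a trait that marks people who would have improved on sham plus therapy. The trial already enrols the arm needed to tell these cases apart. At stake is the interpretation of a secondary aim, not the primary efficacy comparison.

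**Working it through.** **No plan figure to reproduce.** Section 7.2 gives 116 participants in total. The available text gives no sample size, responder definition or model for Aim 3, and no alpha, power, SD or dropout for the trial.

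**Inputs.** From the documents: 116 randomised. Assumed: equal allocation, so 116/2 = 58 per arm (section 8.4 does not state the ratio); mean drop in pain of 1.0 on placebo and 2.3 on IM PNS; SD of the drop 2.3; two-sided alpha 0.05. A responder is taken as a drop of at least 2 points. That is the definition section 21.21 reports for an earlier post-stroke trial, not one stated for this trial.

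**Model.** Drop = 1.0 + 1.3 × arm + 2.3 × (r·x + √(1 − r²)·e), where x is a standardised trait and e is standard normal noise. A prognostic trait has the same r in both arms. An effect modifier has r in the active arm and 0 in the control arm. There were 6,000 simulated trials per setting, so the Monte Carlo standard error is at most √(0.25/6000) = 0.6 percentage points.

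| Test | Trait | r = 0.3 | r = 0.4 | r = 0.5 |
|---|---|---|---|---|
| Responder contrast, active arm | prognostic | 44% | 69% | 90% |
| | modifier | 44% | 69% | 89% |
| Slope on continuous drop, active arm | prognostic | 64% | 88% | 98% |
| | modifier | 64% | 88% | 99% |
| Arm-by-trait interaction, both arms | prognostic | 5% | 5% | 5% |
| | modifier | 36% | 58% | 80% |

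The agreement within the active arm is a matter of logic, not chance: the two kinds of trait generate the same data in that arm, so no analysis confined to it can separate them. The continuous slope shows that dichotomising is not the cause. The active-arm percentages are detection rates for real associations, not error rates for Hypothesis 3.

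**Hand check of the interaction.** In SD units the standard error of the difference in slopes is about √[((1 − r²) + 1)/58]. At r = 0.3 this is √(1.91/58) = 0.181, so the ratio is 0.3/0.181 = 1.65 and power is about 38%. At r = 0.5 it is √(1.75/58) = 0.174, ratio 2.88, power about 82%. Both are close to the simulated 36% and 80%.

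**Precision of the interaction.** For a trait present in half of each arm there are four cells of 29.
- Standard error: √(4/29) = 0.371 SD.
- Detectable at 80% power, alpha 0.05: (1.960 + 0.842) × 0.371 = 1.04 SD, or 1.04 × 2.3 = 2.4 points.
- Overall treatment effect, for comparison: 2.802 × √(2/58) = 0.52 SD.
- 95% confidence interval for the interaction: about ±0.74 SD (1.7 points).
- With 15% loss (assumed, 49 per arm), the detectable interaction rises to 1.13 SD.

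**The case against.** The strongest objection is that no Aim 3 analysis is visible. Section 10.3 defers to an attachment that was not available here, and the restriction to the active arm is inferred from the aim's wording. Section 7.2 does not say who the non-responders are, and relief from treatment with IM PNS could be read as relief attributable to it. Section 8.4 also does not limit the Aim 3 measures to one arm. All of this stands. A reader might infer that the plan analyses the IM PNS arm alone, or omits an Aim 3 model; the documents support neither statement.

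A reader might also infer that an active-arm result has no bearing on patient selection. That is too absolute. A phenotype that reliably fails to improve on stimulation plus therapy is relevant to whether a lead is offered. What fails is crediting the difference to stimulation.

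Regression to the mean after the entry threshold for worst pain (section 9.1) is a tempting further argument. It is not relied on: entry pain is confirmed at Visit 1, baseline outcomes are taken at a separate Visit 2 (sections 8.6 and 9.3), and the simulation contains no threshold.

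Finally, every effect input is assumed, and the rejection rates come from a model without covariates, whereas the recommendation is for adjusted estimates. That limits the numbers to illustration. Low interaction power is a real cost, but the active-arm test gains its power by answering a different question.

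**Conclusion.** The point holds in a conditional form. It is certain that Aim 3 and Hypothesis 3 name no placebo comparison, that Hypotheses 1 and 2 do, and that the secondary objective draws conclusions about mechanism and selection that need one. It is also certain that a contrast confined to the IM PNS arm cannot separate prognosis from modification of the stimulation effect. Whether the analysis is so confined is unknown until the attachment is read.

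The size of any resulting error cannot be estimated from the documents. The illustration shows only that, at 58 per arm, the active-arm contrast does not discriminate at all between the two kinds of trait, while the interaction does so with modest power. This concerns a secondary aim. It is worth correcting because the better analysis uses an arm already enrolled.

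**What to change.** State that Aim 3 estimates how baseline characteristics modify the effect of IM PNS versus placebo on change in BPI 3.

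- Estimate arm-by-trait interactions in all randomised participants with the trait measured, adjusted for baseline pain and the stratification factors (site, baseline pain category, pain duration).
- List in advance a short set of traits covering the six domains that Aim 3 names: psychological, mood, demographic, examination, structural and sensory.
- Report the interactions as exploratory estimates with 95% confidence intervals.
- If a responder contrast is kept, report it in both arms, and label within-arm associations prognostic.
- Limit the sentence on mechanism and patient selection in the secondary objective to what these estimates can show.
- Report the number with structural traits by arm and site. Section 8.4 plans MRI for all, but section 9.2 exempts those with a contraindication, sections 9.3 and 10.1 make its use depend on availability, and section 21.24 labels the MRI visit as one site only. The documents give no figure for how many will have it.

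If the attachment already uses the placebo arm in this way, only the wording of Aim 3 and of the secondary objective needs to change. Otherwise the analysis plan changes too. No new participants or procedures are needed. The cost is low precision, so a non-significant interaction would not show that a trait is irrelevant, and the report should say so.

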8.5 Does this study only involve the use of existing/retrospective data/specimens?
No

8.6 Describe in detail the study design also known as the experimental flow. Include all study procedures a subject will go through, in order of sequence and timing, including frequency of visits, duration of visits, length of subject participation etc. Please Note this needs to be written for an educated person who is not an expert in the field, do not exceed 300 words:
The duration of each subject's participation will be ~8 months.

Visit 1 – Consent/Eligibility: Consent form signed. Assessed for eligibility per inclusion/exclusion criteria. , MRI(prn per exclusion criteria) . BDI, PCS & FABQ administered. BPI administered. Medical history, demographics, comorbidities, and medication use recorded. Pregnancy test (in applicable subjects). (~4 hrs)

Visit 2 – Baseline Outcomes Assessment: Study outcomes assessment measures (see Outcomes Assessment) administered to establish baseline levels. (~4 hrs)

NOTE: VISITS 3 THROUGH 10 WILL OCCUR DURING A 60 DAY WINDOW +/- 5 days.

Visit 3 - BPI administered. Subject queried for medication usage and adverse events. Sprint MicroLead (Electrode) Implant Procedure: Testing of muscle response with Sprint Test Needles; Implantation of percutaneous Sprint MicroLead. Subject given instructions on care of Lead exit site and bandage change instructions. Randomization to treatment group. Physical Therapy Treatment (~2.5 hrs)

Visit 4 –BPI administered. Post-Implant Safety Check. Check the Lead exit site and dressing change(prn). Start of Stimulation: Programming of external stimulator (Sprint Stimulator). Subject given instructions on use of System and care of Lead exit site. Subject queried for medication usage and adverse events. Physical Therapy Treatment (~1.5 hours)

Visit 5-10 Therapy Visits: Skin check/dressing change(prn), medication and adverse events query.

Visit 11 - EOT Outcomes Assessment & Explant Procedure: BPI, SF-12, SPADI & PGIC administered. Skin checked. Study outcomes assessment measures administered. Subject queried for medication usage and adverse events. Lead Removed. X-rays performed (may be done as separate clinical visit). (~3 hrs)

Phone call: Post-Explant check up. (15 min): Queried about skin and x-ray results reviewed.

Visit 12 - End of Treatment + 12 wks Outcomes Assessment: Skin checked. Study outcomes assessment measures administered. Subject queried for medication usage and adverse events. (~2 hrs)

Visit 13 – End of Treatment + 24 wks Outcomes Assessment: Skin checked. Study outcomes assessment measures administered. Subject queried for medication usage and adverse events. (~2 hrs)

Provision for lead replacement: If, in the judgement of the Investigator, the Sprint MicroLead becomes significantly displaced or fully dislodged, it is possible that the Investigator may elect to place another lead which would require an unscheduled visit. Other visits may be repeated as appropriate.

Unscheduled Visits are conducted if/as needed.

*some visits may be combined to accommodate subject or staff scheduling

*Visits may be completed via telephone, telehealth or email as determined by the principle investigator in case of immediate hazard to the subject

Check yes or no.

This is also known as NIH Experimental Procedure section or Clinical Trial Procedure/Experimental Flow section. Do not just attach documents in response to this question you must do a study design summary for IRB Review.

*Visits 12 and 13 : These visits include questionnaires and can be completed via telehealth, telephone or email at the discretion of the PI

Email will only be used with subject who sign the Alternative Means HIPAA

8.7 Please attach study design/subject visit schedule here:

Name

[PNS for SIS Visit Schedule Table](#) | [History](#)

Description

If you have an electronic schedule of study visits and/or procedures please attach here.

View: 09-00 Inclusion/Exclusion Criteria

9.0 Inclusion/Exclusion Criteria:

9.1 What are the inclusion criteria? Put this information in bullet form:

- Shoulder pain of >3 months
- Age>=21-90
- Worst pain in the last week>=4 (0-10 scale)
- Ability to check skin and perform dressing changes, independently or with assistance
- Stable dose of pain medication (Not taking more than 1 opioid or 1 non-opioid analgesic)

Please list inclusion criteria.

9.2 What are exclusion criteria? Put this information in bullet form:

- Current shoulder joint or overlying skin infection, or current bacterial infection requiring antibiotics
- Other chronic pain syndrome (Pain in another area of the body 15 or more days in the last 30 (more than half of the time) or taking daily analgesics for another pain syndrome)
- Prior shoulder surgery to ipsilateral shoulder joint (glenohumeral, rotator cuff, AC joint, etc.)
- Corticosteroid injection in the ipsilateral shoulder or any pain relieving procedure at the shoulder in the last 12 weeks
- Uncontrolled bleeding disorder
- Medical instability based on physician opinion after review of medical information
- Pregnancy
- Neurological condition affecting ipsilateral upper limb (add (such as central neurologic injury/illness, active radiculopathy, diabetic amyotrophy, Complex Regional Pain Syndrome, etc.)
- Current Worker's compensation claim for the ipsilateral shoulder
- Diagnosis of shoulder instability, adhesive capsulitis or severe glenohumeral OA based on current patient symptoms and physical examination
- Ipsilateral shoulder injury due to severe trauma (Fall from greater than standing height; Motor vehicle crashes; Struck by vehicle or other fast-moving projectile (e.g., bullet, baseball, etc.); Assault (i.e., injuries intentionally inflicted by another person))
- osseus fracture in ipsilateral arm in the last year
- Ipsilateral upper limb amputation other than a single digit (digits 2-5, partial or full)
- Patient is a candidate for shoulder surgery based on physician opinion
- Compromised immune system (immunodeficiency or immunosuppression)
- Current use of a Deep Brain Stimulation (DBS) system, implanted active cardiac implant (e.g. pacemaker or defibrillator), any other implantable neuro-stimulator whose stimulus current pathway may overlap with that of the SPRINT System
- Patients who have a tape or adhesive allergy
- Contraindication to MRI (metal in body, claustrophobia, body habitus, etc) – exclude from MRI only
- Severe problems with maintaining follow-up expected (such as but not limited to history of substance abuse, homelessness/incarceration, dementia, brain injury, and psychotic disorders)

Please list exclusion criteria.

